### **PROTOCOL FORM / RESEARCH DESCRIPTION**

If an item does not apply to your research project, indicate that the question is "not applicable" – do not leave sections blank

**Click once on the highlighted entry in each box to provide your response.** Click the item number/letter or word, if hyperlinked, for detailed instructions for that question. If your response requires inserting a table, picture, etc, you may need to first delete the box that surrounds the answer and then insert your table or other special document.

#### **1. Purpose and objectives.** List the purpose and objectives:

The purpose of this trial is to evaluate the symptomatic benefits of immunomodulatory treatment with IVIG for POTS (postural tachycardia syndrome) patients with evidence of autoimmunity.

#### **Specific aims:**

Our primary aim is to determine if treatment with IVIG (Gammunex-C) is superior to active placebo (intravenous albumin) in improving the symptoms of POTS.

We propose a double-blind placebo controlled crossover pilot study of IVIG for the treatment of POTS. We will enroll subjects who meet the consensus criteria for POTS diagnosis (Sheldon et al. 2015) who have moderate to severe symptom burden and also have clinical or laboratory evidence of autoimmunity.

Secondary aims are to determine if IVIG treatment improves objective clinical measures and to evaluate the utility of clinical and laboratory measures to identify patients most likely to respond to therapy

#### 2. Background.

- Describe past experimental and/or clinical findings leading to the formulation of your study.
- For research involving investigational drugs, describe the previously conducted animal and human studies.
- For research that involves FDA approved drugs or devices, describe the FDA approved uses of this drug/device in relation to your protocol.
- Attach a copy of the approved labeling as a product package insert or from the Physician's Desk Reference.

You may reference sponsor's full protocol or grant application (section number and/or title) or if none, ensure background includes references.

Please respond to all components of this item, or clearly indicate which components are not applicable.

#### a. Background

Postural tachycardia syndrome (POTS) is the most common autonomic disorder (Low et al. 2009) with prevalence estimated at 170/100,000 in the United States (Schondorf et al. 1999). POTS appears to be a heterogeneous syndrome that can arise from multiple distinct mechanisms and has been divided into several subtypes based on these proposed mechanisms (Benarroch 2012). One subtype is referred to as neuropathic subtype which describes the group of POTS with evidence of peripheral denervation in their lower extremities (Benarroch 2012). Evidence of peripheral nerve dysfunction can be detected on neurologic exam, through sudomotor testing and/or skin biopsy to evaluate intraepidermal small nerve fiber density. Within the neurogenic subgroup, a smaller subset may have an underlying autoimmune mechanism contributing to the development of both the neuropathy and POTS. These patients may report a preceding viral illness or other physiological stressor (such as immunization, pregnancy, injury, or minor surgery), may have elevated levels of one or more serum autoantibodies, co-existing

autoimmune disorders (including Sjogren's syndrome), or other clinical features suggesting autoimmunity (Thieben et al. 2007). A review of 100 POTS patients showed that there was higher prevalence of autoimmune markers and co-morbid autoimmune disorders in POTS patients compared to the general population with 25% having positive ANA, 7% with antiphospholipid antibody and 20% with co-morbid autoimmune disorders (Blitshteyn 2015).

Gammunex-C, a form of intravenous immunoglobulin (IVIG), is approved for the treatment of chronic inflammatory demyelinating neuropathy (CIDP) or idiopathic thrombocytopenic purpura (ITP) (see attached package insert). IVIG has been in use for many decades in the treatment of these disorders and many other inflammatory/autoimmune diseases. It is generally very safe and well tolerated. More recently, IVIG has been proposed as an effective treatment for presumed inflammatory neurological disorders which do not meet the criteria for CIDP. Specifically, case reports and cases series have indicated therapeutic responses to IVIG in autonomic neuropathies. (See Goodman, B. P. (2017). "Immunoresponsive Autonomic Neuropathy in Sjogren Syndrome-Case Series and Literature Review." Am J Ther doi: 10.1097/MJT.00000000000583. and Oaklander, A. L. (2016). "Immunotherapy Prospects for Painful Small-fiber Sensory Neuropathies and Ganglionopathies." Neurotherapeutics 13(1): 108-117).

Intravenous Albumin is approved for the treatment of hypovolemia (see attached package insert). The use of albumin to increase plasma volume in patients with POTS has been suggested. In this study, albumin will be used as an active control treatment to provide the same volume and protein load as IVIG but without the immunomodulatory effects.

Significance: There have been few well designed clinical therapy trials aimed at POTS patients and even fewer that are aimed at a particular pathophysiological subtype of POTS. Evidence suggests that POTS is a heterogeneous disorder with differing underlying mechanisms. Several uncontrolled case series have suggested a benefit of IVIG for POTS, but the volume expansion associated with infusion of IVIG make it difficult to assess the immunomodulatory effects of this treatment. We propose to evaluate the efficacy of IVIG using a double-blind randomized cross over design that will determine efficacy while reducing effects of inter-subject variability and placebo effect which are common problems in POTS therapy research. Even with the statistical advantages of a crossover design, the treatment cohort will be small, and this study is designed to be a pilot (phase II) study to evaluate the feasibility, tolerability and potential benefits of treatment. The results of this pilot study will provide the impetus and rationale for a larger multicenter clinical trial to definitively evaluate immunomodulatory treatment in POTS.

#### b. Current practice

Currently there are no pharmacological treatments for POTS that have proven efficacy in randomized controlled trials.

#### 3. Study Design.

Describe the study design (e.g., single/double blind, parallel, crossover, etc.) Consider inserting a scheme to visually present the study design.

This will be a double-blind placebo controlled crossover study. See Schedule of study procedures below for time line:

|   | Screen | Baseline |   |   |    |    |     | Т  | reat | men | t ver | sus Act | tive C | ompa | rator | · (Alb | umin) | )   |     |     |     |                | Follo | ow-up |
|---|--------|----------|---|---|----|----|-----|----|------|-----|-------|---------|--------|------|-------|--------|-------|-----|-----|-----|-----|----------------|-------|-------|
| Study Weeks                             | -2     | -1       |   | 0-4 5-7 9-11 12-17 17-20 22-24 26-28 30 |    |    | 32  | 34 |      |     |       |         |        |      |       |        |       |     |     |     |     |                |       |       |
| Treatment #                             |        |          |   | 1-                                      | 4* |    | 5-6 | 5  | 7    | -8  | v     | Vashou  | ut     |      | 1     | -4     |       | 5   | -6  | 7   | -8  | Final
Visit |       |       |
| Study day                               | -14    | -7 to 0  | 0 | 7                                       | 14 | 21 | 35  | 49 | 63   | 77  | 91    | 105     | 118    | 119  | 126   | 133    | 140   | 154 | 168 | 182 | 196 | 210            | 224   | 238   |
| Informed Consent                        | Х      |          |   |   |    |    |     |    |      |     |       |         |        |      |       |        |       |     |     |     |     |                |       |       |
| Medical History                         | Х      |          | - |   |    |    |     |    |      |     |       | Х       |        |      |       |        |       |     |     |     |     |                |       |       |
| Vital signs, physician
exam          | х      |          |   |   |    |    |     |    |      |     |       | х       |        |      |       |        |       |     |     |     |     |                |       |       |
| Inclusion/Exclusion
Criteria         | х      | x        |   |   |    |    |     |    |      |     |       | х       | Х      |      |       |        |       |     |     |     |     |                |       |       |
| Pregnancy Test              |        | Х        |   |   |    |    |     |    |      |     |       |         | Х      |      |       |        |       |     |     |     |     |                |       |       |
| Autonomic testing           | Х      |          |   |   |    |    |     |    |      |     |       | Х       |        |      |       |        |       |     |     |     |     | Х              |       |       |
| Pupillometry                | Х      |          |   |   |    |    |     |    |      |     |       | Х       |        |      |       |        |       |     |     |     |     | Х              |       |       |
| Serological testing         | х      |          |   |   |    |    |     |    |      |     |       | Х       |        |      |       |        |       |     |     |     |     | Х              |       |       |
| Skin Biopsy⁵                            | Х      |          |   |   |    |    |     |    |      |     | X6    |         |        |      |       |        |       |     |     |     |     | X⁵             |       |       |
| Supine and standing
catecholamines   | х      |          |   |   |    |    |     |    |      |     | Х     | х       |        |      |       |        |       |     |     |     |     | х              |       |       |
| Standing vitals                         | Х      | Х        |   |   |    |    | Х   |    |      |     | Х     | Х       | Х      |      |       |        |       | Х   |     |     |     | Х              |       |       |
| VOSS                                    | х      | Х        |   |   |    |    |     |    |      |     | х     | Х       | Х      |      |       |        |       |     |     |     |     | Х              |       |       |
| ECG                                     | х      |          |   |   |    |    |     |    |      |     |       |         |        |      |       |        |       |     |     |     |     |                |       |       |
| COMPASS 318                             | х      | Х        |   |   |    |    |     |    |      |     | х     | Х       | Х      |      |       |        |       |     |     |     |     | Х              | Х     | Х     |
| Quality of Life
questionnaire (SF36) | х      | х        |   |   |    |    |     |    |      |     | х     | х       | х      |      |       |        |       |     |     |     |     | х              | х     | х     |
| Fatigue score                           | Х      | Х        |   |   |    |    |     |    |      |     | Х     | Х       | Х      |      |       |        |       |     |     |     |     | Х              | Х     | Х     |
| Symptom score                           | Х      | Х        |   |   |    |    |     |    |      |     | Х     | Х       | Х      |      |       |        |       |     |     |     |     | Х              | Х     | Х     |
| COMPASS-change                          |        |          |   | Х                                       |    | Х  | Х   | Х  | Х    | Х   | х     |         | Х      |      | Х     |        | Х     | Х   | Х   | Х   | Х   | Х              |       |       |
| Return daily diary          |        | Х        |   | Х                                       |    | Х  | Х   | Х  | Х    | Х   | Х     |         | Х      |      | Х     |        | Х     | Х   | Х   | Х   | Х   | Х              |       | Х     |
| Study Infusion                          |        |          | Х | Х                                       | Χ  | Х  | Х   | Х  | Х    | Х   |       |         |        | Х    | х     | Х      | Х     | Х   | Х   | Х   | Х   |                |       |       |
| Subject impression                      |        | Х        |   |   |    |    |     |    |      |     | Х     |         | Х      |      |       |        |       |     |     |     |     | Х              |       | X     |
| Concomitant Medications                 |        | Х        |   |   |    |    |     |    |      |     | Х     |         | Х      |      |       |        |       |     |     |     |     | Х              |       | Х     |
| Adverse Events                          |        |          |   |   |    |    |     |    |      |     | х     |         | Х      |      |       |        |       |     |     |     |     | Х              |       | Х     |
| Safety Labs (CBC/BMP)       | Х      |          |   |   |    |    |     | Х  |      |     | Х     |         | Х      |      |       |        |       |     | Х   |     |     | Х              |       |       |
| Telephone call*                         |        |          |   |   |    |    |     |    |      |     |       | х       |        |      |       |        |       |     |     |     |     |                | х     | Х     |

1. Serum or urine pregnancy test for women of childbearing potential

2. Blood testing includes: Complement C3/C4, quantitative immunoglobulins, gAChR, ANA, ENA, APLA, gliadin antibody, transglutaminase antibody, CRP

3. Daily diary will be picked up at every infusion

4. Safety labs: complete blood count (CBC) with differential, basic metabolic panel

5. Skin biopsy is not required. Results can be used if done within the last year. If no results available, PI discretion if biopsy is indicated.

. Repeat skin biopsy assessment if needed can be done between 2-4 weeks after last infusion.

7. Within the past 12 months.

 Collected by online survey via RedCap

\*Patients will follow structured exercise regimen, water and salt recommendations throughout 30 weeks \*Infusion of study drug or albumin would occur on weeks 0, 1, 2, 3, 5, 7, 9, 11 (+/- 2 days) during part 1 and on weeks 17, 18, 19, 20, 22, 24, 26, 28 (+/- 2 days) during part 2. There will be a 6 week washout between weeks 11 and 17 and after week 28. Total study duration of 34 weeks

Abbreviations: complete blood count (CBC), basic metabolic panel (BMP)

\*Clinic visits are highlighted in grey and infusion visits are white

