We will be following the Aston infusion center IVIG solution Infusion order. Patients will receive premedication's with 10mg of Cetirizine (Zyrtec) by mouth and 500 mg Acetaminophen (Tylenol) by mouth 30 min. (+/- 5 min) prior to infusion. After premedication and placement of peripheral IV, they will receive D5W 25 mL IV at 300 mL/hour (immediately before infusion). Then the patients will receive study medication in a blinded fashion. The dose of medication will be 0.4 g/kg (either Gammunex-C, 10% or Albumin, 10%). The dose will be rounded to the nearest 5 grams, and the dose will remain constant for each of the 8 study infusions even if weight changes. Since albumin is packaged at a 20% solution, this drug will be diluted to 10% using D5W prior to infusion. The prepared study drug dose will be provided by the research pharmacist in packaging marked with the study subject identifier and infusion number but will have no identifiers to indicate the drug identity (infusion nurse, patient and study coordinator must remain blinded to the treatment assignment). Infusion rate will start at 0.6 ml/kg/hour and may be increased by 0.6 ml/kg/hour every 15 min as, tolerated, to a maximum infusion rate of 210 ml/hour. Subsequent infusion rates may be started at the tolerated rate. Start and stop times and infusion rates will be recorded in the study log. Vital signs will be recorded at the start and end of the infusion and at the time of any changes of infusion rate or clinical symptoms. Once the study infusion is complete, the infusion nurse will alert the study coordinator, and the coordinator will check on the patient for any emergent AEs.

Post infusion, the intravenous catheter will be flushed with D5W 25 mL IV at 300 ml/hour and then the catheter will be removed. Once the coordinator check is complete the patient can be discharged.

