Neither the patient nor the examiner will know if they are receiving IVIG or albumin until after the study is over. Patients in the study will be asked to complete a diary entry every day during the duration of the study (includes fluid intake, minutes of exercise, daily symptom score, and perceived side effects). More detailed assessment will be made at beginning, mid-point washout and end of study with including stand test, supine and standing catecholamine levels, COMPASS-31, fatigue score, quality of life score and symptom scores. Skin biopsy will be repeated at the assessment if the biopsy was performed at baseline and was abnormal.

Assessments will be made on days -1, 84, 111 and 196, with stand test, and supine and standing catecholamine levels. Symptom surveys COMPASS-31, Quality of Life questionnaire (SF-36), fatigue score, and symptoms score will be repeated at days -14, -1, 84, 98, 111, and 196. The VOSS score will be be performed at screening, baseline, all visits during the washout phase, and at final visit. The analysis will compare responses in the IVIG and placebo groups including individual comparisons between treatment and placebo and group comparisons. A specialized repeated measures analysis will be used to separate the effects of time, treatment and sequence of treatment in this cross-over design.

The primary outcome will be change in COMPASS-31 score (Sletten et al. 2012) (Rea, Campbell, and Cortez 2017). Because both treatments will expand plasma volume, we anticipate that both the IVIG and albumin groups will result in improvement in the COMPASS-31 orthostatic intolerance (OI) subscore. Accordingly, we will analyze the change in both the total COMPASS-31 scores and the score with the OI subscore removed.

Secondary outcomes will be patient subjective responses, reported activity level and objective measures including orthostatic tachycardia, supine and standing catecholamine profiles and skin biopsy results (nerve fiber density). The randomized crossover design will help reduce the confounding factors of interindividual symptom reporting variability and confounding effect of activity level on symptoms and drug carryover from phase 1 to phase 2 of the study. We will subsequently perform post hoc analysis comparing responders to non-responders to determine if baseline characteristics can identify subjects most likely to respond to this intervention.

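### Could an immunoglobulin result at day 105, in the washout, unblind the second treatment phase?

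*Protocol*

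**What the plan says.** The schedule in protocol section 3 has a row for "Serological testing" marked at days -14, 105 and 210. The row carries footnote 7, which reads "Within the past 12 months". Footnote 2 lists the blood panel, "Complement C3/C4, quantitative immunoglobulins, gAChR, ANA, ENA, APLA, gliadin antibody, transglutaminase antibody, CRP", but no footnote 2 marker appears in any table row as we have it. Infusions run on days 0 to 77 and 119 to 196.

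On blinding, protocol section 4.a says that "infusion nurse, patient and study coordinator must remain blinded to the treatment assignment" and that "Neither the patient nor the examiner will know if they are receiving IVIG or albumin until after the study is over". The SAP's second paragraph says participants and investigators remained blinded through phase 2. Section 5.b gives abnormal safety laboratory results and adverse events to a safety officer. Safety labs are defined as a blood count and basic metabolic panel, so immunoglobulins are not among them. Nothing says who receives serology results.

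The SAP also says that phase 2 was not part of the primary outcome and was analysed separately, with 23 of 30 participants.

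**The concern.** One product is immunoglobulin and the other is albumin. A quantitative immunoglobulin result taken in the washout includes whatever infused immunoglobulin remains, so a rise since screening would suggest that IVIG came first. In a two-product crossover that also reveals the second product.

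Day 105 carries an eligibility check and a physician examination as well, so blinded staff could plausibly be looking at the chart. If they or the patient drew the inference, the patient-reported outcomes of phase 2, and the protocol's crossover analysis that uses both phases, would rest on weaker blinding than the SAP states.

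**Working it through.** **1. Timing.** Matching the row cells to the 24-column day header gives serology at days -14, 105 and 210. The last phase 1 infusion is in week 11 (11 × 7 = day 77) and the first of phase 2 in week 17 (17 × 7 = day 119). So the draw would fall 105 − 77 = 28 days after phase 1 dosing and 119 − 105 = 14 days before phase 2 dosing.

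**2. Does a day 105 serology draw take place?** The documents point both ways.

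For:
- The mark itself. Day 105 also has marks for the physician examination, autonomic testing, standing vitals and the row beginning "Supine and standing" (catecholamines).
- The procedure-count table (item 4.d) gives autonomic testing as 1 + 2 = 3, which equals its three schedule marks (-14, 105, 210) under the same footnote 7. That footnote therefore need not cancel a repeat. The physical examination count of 1 + 1 = 2 likewise equals its marks at days -14 and 105.
- Section 5.a puts safety labs at weeks 2, 8, 15 and 24, and 15 × 7 = 105.
- Section 4.a says "More detailed assessment will be made at beginning, mid-point washout and end of study with including stand test, supine and standing catecholamine levels".

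Against:
- Day 105 is marked "Telephone call", as are the follow-up contacts at days 224 and 238.
- The next paragraph of section 4.a puts the stand test and catecholamines on days -1, 84, 111 and 196, and names day 98 only for surveys. Taken in order, 84, 98, 111 and 196 correspond to the schedule's 91, 105, 118 and 210. That alignment is an inference, but it makes the counterpart of day 105 survey-only. Neither paragraph lists mid-point serology.
- Under footnote 7 a day -14 result would still be in date at day 105 (105 + 14 = 119 days) and at day 210 (210 + 14 = 224 days).
- Item 4.d counts labs as 1 + 5 = 6. The schedule already has six safety-lab days (-14, 49, 91, 118, 168, 210), leaving no room for a separate day 105 panel. This match is itself shaky, because section 5.a lists different weeks.

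**3. What outcome data come after day 105?** COMPASS-31 is marked at days -14, -7 to 0, 91, 105, 118, 210, 224 and 238, so four of eight entries come later. COMPASS-change is marked on 15 days, eight of them after day 105 (118, 126, 140, 154, 168, 182, 196, 210). The end-of-phase-1 COMPASS-31 at day 91 is 105 − 91 = 14 days before the draw.

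**4. How informative could the result be?** The documents give no half-life, so this is a range under assumption. With 0.4 g/kg at each of eight infusions (8 × 0.4 = 3.2 g/kg) and half-life h days, the residue at day 105 is Σ 0.4 × 2^(−(105 − t)/h) over t = 0, 7, 14, 21, 35, 49, 63, 77.

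| Assumed h (days) | Residue (g/kg) | Share of 3.2 g/kg |
|---|---|---|
| 7 | 0.033 | 1% |
| 14 | 0.204 | 6% |
| 21 | 0.435 | 14% |
| 35 | 0.885 | 28% |

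The residue runs from almost nothing to more than two full infusions (0.885 / 0.4 = 2.2). Turning it into a rate of correct guesses needs two more assumptions: distribution volume (0.08 to 0.12 L/kg) and the SD of the change since screening (1 to 3 g/L). With Φ(difference / (2 × SD)), the rate runs from 52% (h = 7, 0.12 L/kg, SD 3) to over 99% (h = 35, 0.08 L/kg, SD 1), where 50% is chance. A range that wide shows that the documents cannot settle the question. The assay also measures total immunoglobulin, the patient's own included, so only a change from screening carries any signal.

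**The case for a change.** The strongest case for acting is that the schedule is the most specific statement of what is done when, and it marks the test. The autonomic-testing count shows that marks under footnote 7 can be real repeats. The panel contains an analyte that the study drug raises, and the reader cannot verify the SAP's statement about phase 2 blinding. One sentence sending the result to an unblinded role would cost almost nothing.

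Much of this stands. A repeat is plausible, linking the panel to the serology row is the natural reading, and no text covers the handling of the result.

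It falls short on three counts. First, the draw is unproven, because the schedule, sections 4.a and 5.a and the count table were never reconciled. Second, a stated duty to keep named people blinded already obliges the team to keep a revealing result from them, and the protocol has an unblinded pharmacist and a safety officer outside the assessments. Third, the SAP is dated October 2023 and reports the phase 2 analysis in the past tense, so a routing rule would probably have nothing left to protect. What remains is at most a sentence of disclosure in the report.

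**Conclusion.** No change to the plan is needed. The gap is an unwritten operating detail beneath a blinding requirement that both documents state, and it depends on a blood draw that the documents support and contradict in about equal measure. The mismatch over day 105 is a clerical inconsistency between the schedule and the narrative.

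The primary result is untouched, provided phase 1 change is read at the end-of-phase-1 visit (day 91 in the schedule, day 84 in section 4.a), which the SAP does not date explicitly. Any exposure is confined to four of eight COMPASS-31 and eight of fifteen COMPASS-change entries, in the 23 participants who entered phase 2. The SAP analyses those data separately from the primary outcome, although the protocol's crossover analysis would use them. An investigator who sees the value does not thereby unblind a patient who completes COMPASS-31 online, and no bias in COMPASS-31 points has been shown. Whether the result would be revealing at all depends on an assumed half-life, volume and variability.
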